4.2. Sample Size Justification

Approximately 200 subjects 50-80 years old inclusive will be enrolled across US or, if needed, other countries at 5-15 sites. The subjects will be randomized in a 3:1 ratio receiving either the

PB2452 investigational study drug or placebo. Hence, a total of approximately 150 subjects will be receiving PB2452 and approximately 50 subjects will be receiving placebo.

The primary efficacy endpoint will be assessed by comparing the minimum % inhibition of PRU assessed by VerifyNow within 4 hours after the initiation of study drug between PB2452 group vs placebo group. A sample size of approximately 200 subjects with 3:1 allocation ratio (PB2452:placebo) will provide > 99% power to detect a mean difference of 15 in % inhibition of PRU between PB2452 and placebo group using a two-sided two-sample t-test with type I error of 0.05 (a standard deviation of 20 for % inhibition is assumed within each treatment group, which is obtained from previous studies). The sample size of 200 (150 active vs 50 placebo) will provide substantial safety information on PB2452 in older and elderly healthy subjects.

Subjects who withdraw from the study and who do not have adequate collection of safety, hemodynamic and pharmacokinetic samples for evaluation of safety, PK, and PD profiles may be replaced at the discretion of the Sponsor. Any replacement subject will be assigned to receive the same treatment as the subject he or she is replacing.

4.3. Randomization, Stratification, and Blinding

As described above, subjects will be randomized in a 3:1 (PB2452:placebo) ratio. The randomization will be employed via Medidata's RTSM, a central Interactive Web Response system (IWRS). No stratification will be utilized.

This is a double-blind study. Neither the subjects nor the investigator will be aware of the treatment assignment. Blinding will be maintained throughout the study by use of active and placebo dose forms prepared to be similar in appearance. To maintain the blind, only designated pharmacy staff at the study site will have access to the randomization code.

The study blind will be broken on completion of the clinical study and after the study database has been locked. If necessary (e.g., information required for enrolment in a subsequent study), a request may be submitted to the Sponsor to receive study treatment assignment for a subject.

4.4. Primary Statistical Hypothesis

The primary objective of the study is to assess the estimand defined as the comparative treatment effect in reversal of the antiplatelet effects of ticagrelor in all subjects randomly assigned to study treatment, who take any amount of study drug and have at least one measurable post dose PRU value (i.e. the modified ITT (mITT) population as further detailed in Section 5).

The reversal will be assessed by the primary study endpoint of minimum % inhibition of PRU assessed by VerifyNow within 4 hours after the initiation of study drug. Percent inhibition of PRU is calculated as $100 * [(PRU_{bsl} - PRU_{trt})/PRU_{bsl}]$ where PRU_{bsl} refers to the PRU value measured before treatment with ticagrelor and PRU_{trt} refers to the PRU value measured posttreatment with the study drug.

The analysis will test whether PB2452 is superior to Placebo according to the following Null (H_0) and Alternative (H_1) statistical hypotheses:

$$H_0: \Delta = 0 \quad \text{vs.} \quad H_1: \Delta \neq 0$$

where $\Delta = \mu_{\text{PB2452}} - \mu_{\text{placebo}}$ with

μ_{PB2452} = population mean minimum %inhibition of PRU in the PB2452 arm, and

μ_{placebo} = population mean minimum %inhibition of PRU in the placebo arm

4.5. Estimated Duration of Subject Participation and Follow-up

The study will consist of a Screening period (Days -45 to -4), a Check-in day (Day -3), a pre-treatment period (Day -2 and -1), an on-site Randomization/Treatment day (Day 1), a 2-day on-site Follow-up period (Days 1 through 3), a Day 7 Follow-up visit, and a final Follow-up visit (Day 35+3 days). The estimated duration of the study for each subject, excluding screening, is approximately 35+3 days.

5. ANALYSIS POPULATIONS

The results from this study will be presented using the following populations: For purposes of analysis, the following populations are defined:

Population	Description
All Subjects	All subjects who sign the Informed Consent Form (ICF).
Intention-to-Treat Population	All randomized subjects.
Modified Intention-to-Treat Population	Modified Intention-to-Treat (mITT) population includes all subjects randomly assigned to study treatment, who take any amount of study drug (PB2452 or placebo). Subjects will be analyzed as treated.
Safety Population	The Safety Population includes all subjects who have received any amount of study drug (PB2452 or placebo). The Safety Population will be analyzed for all safety assessments. Subjects in the Safety population will be analyzed as treated.
Per Protocol Population	The Per Protocol (PP) population includes subjects in the mITT Population who do not have major protocol deviations and who complete the study. Protocol deviations will be assessed prior to database lock and unmasking. The PP population will be analyzed using observed data only for efficacy variables. Subjects in the PP population will be analyzed as treated.
PK Population	The PK population includes all subjects with a measurable PK sample of the study drug. The PK population will be used to summarize all PB2452 blood concentrations. Subjects in the PK population will be analyzed as treated.

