9.2.2 Analysis Subsets

The results from this study will be presented using the following populations: For purposes of analysis, the following populations are defined:

Population	Description
All Subjects	All subjects who sign the ICF
Modified Intention-to- Treat Population	Modified Intention-to-Treat (mITT) population includes all subjects randomly assigned to study treatment, who take any amount of study drug (PB2452 or placebo). Subjects will be

Population	Description
	analyzed according to the treatment they are randomized to.
Safety Population	The safety population includes all subjects who have received any amount of study drug. The safety population will be analyzed for all safety assessments. Subjects in the Safety population will be analyzed as treated.
Per Protocol Population	The Per Protocol (PP) population includes subjects in the safety population who do not have major protocol deviations and who complete the study. Protocol deviations will be assessed prior to database lock and unmasking. The PP population will be analyzed using observed data only for efficacy variables. Subjects in the PP population will be analyzed as treated.
Pharmacokinetic Population	The PK population includes all subjects with a measurable PK sample of the study drug. The PK population will be used to summarize all PB2452 blood concentrations. Subjects in the PK population will be analyzed as treated.

The statistical analysis of safety data will be performed for the Safety population. The analysis of efficacy data will primarily be performed for the mITT population. The efficacy analysis based on the PP population will serve as sensitivity analyses.

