9.4.2 Specified Analyses for Independent Data Monitoring Committee Review

For this study, there will be no Independent Data Monitoring Committee (DMC).

9.5 **Procedures for Reporting Changes to the Planned Analysis**

The SAP will detail the strategy for statistical analyses for this study. Any change in the plan described in this protocol will be highlighted in the SAP.

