6.3. Missing Data

For subjects with missing data on efficacy endpoints, no imputation will be used. For binary endpoints, the missing data will be excluded from the calculation of proportions.

For the purpose of determining inclusion of AEs in the treatment-emergent AE (TEAE) summary tables, incomplete or missing AE onset and end dates will be imputed as follows:

Incomplete or missing onset dates (where UK and UNK indicate unknown or missing day and month, respectively):

- UK-MMM-YYYY: If the month and year are different from the month and year of the first dose of study drug, assume 01-MMM-YYYY. If the month and year are the same as the first dose of study drug month and year, and the end date (after any imputation) is on or after the dose of study drug, then assume the date of the dose of study drug. If the month and year are the same as the dose of study drug month and year and the end date (after any imputation) is prior to the dose of study drug, then assume the end date for the onset date.
- DD-UNK-YYYY or UK-UNK-YYYY: If the year is different from the year of dose of study drug, assume DD-JAN-YYYY or 01-JAN-YYYY of the onset year, respectively. If

the year is the same as the dose of study drug year, and the end date (after any imputation) is on or after the dose of study drug, then assume the date of the dose of study drug for the onset date. If the year is the same as the dose of study drug, and the end date (after any imputation) is prior to the dose of study drug, then assume the end date for the onset date.

- Missing onset date: If the onset date is completely missing and the end date (after any imputation) is on or after the start of administration of study drug, then assume the onset date to be the start of administration of study drug. If the end date (after any imputation) is prior to the start of administration of study drug, then assume the end date to be the onset date.

Incomplete or missing end dates (where UK and UNK indicate unknown or missing day and month respectively):

- UK-MMM-YYYY: Assume the last day of the month;
- DD-UNK-YYYY or UK-UNK-YYYY: Assume DD-DEC-YYYY or 31-DEC-YYYY, respectively;
- Missing end date: Assume 31-DEC-YYYY, where YYYY is the year of the start of administration of study drug.

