7. SUBJECT DISPOSITION

7.1. Disposition

Subject disposition will be presented for all screened subjects, including number of screen-failed subjects, number of subjects enrolled (i.e. receiving ticagrelor) and number of subjects randomized. For number of subjects randomized, subject disposition will be presented by randomized treatment group and total.

Number and percentage of subjects in the following categories will be summarized as appropriate:

- Screen failed
- Randomized (ITT Population)
- mITT Population
- Safety Population
- Per-Protocol Population
- PK Population

Additionally, a summary of study completion and treatment completion status will be presented along with reasons for discontinuation if any.

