9. EFFICACY

9.1. Analysis of Primary Efficacy Endpoint

All efficacy analyses will primarily be based on the mITT Population. Supportive analyses will be performed based on the ITT and Per-Protocol Population.

The primary endpoint is defined as the minimum % inhibition of PRU assessed by VerifyNow within 4 hours (inclusive) after the initiation of study drug. Percent inhibition of PRU is calculated as $100 * [(PRU_{bsl} - PRU_{trt})/PRU_{bsl}]$, where PRU_{bsl} refers to the PRU value measured before treatment with ticagrelor and PRU_{trt} refers to the PRU value measured posttreatment with the study drug.

Results by treatment groups will be summarized at baseline, at the timepoint where minimum is achieved (nadir), and percent inhibition from baseline using descriptive statistics: number of subjects with non-missing data, mean, standard deviation, median, minimum, and maximum. To complete the clinical picture, the % inhibition of PRU from baseline will be summarized at all time points using descriptive statistics.

Hypothesis testing will also be conducted using a 2-sided two-sample t-test test with a significance level of 0.05 to compare the efficacy of PB2452 and placebo. The corresponding 95% confidence interval will be provided for the mean difference between PB2452 and placebo.

In order to compare the response to the Phase 3 patient study which does not include a pre-ticagrelor baseline, percent inhibition of PRU will also be calculated as $100 * [(180 - PRU_{trt})/180]$, where PRU_{tttttt} refers to the PRU value measured at a given visit following start of study drug infusion. A PRU value of 180 is considered the lower limit of normal (LLN) platelet function, as described in the VerifyNow® P2Y₁₂ PRUTest® manufacturer's user guidance. This alternative calculation will be used to analyze the primary endpoint in an exploratory manner using the methods described above.

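### SAP 5 analyses the primary mITT population as treated, Protocol 9.2.2 analyses it as randomized, and the SAP does not flag the change

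*SAP*

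**What the plan says.** Protocol 9.2.2 and SAP 5 agree on who is in mITT: randomized subjects who received any study drug. They disagree on the arm in which a subject is counted. The protocol has mITT subjects "analyzed according to the treatment they are randomized to". The SAP's mITT row covers randomized subjects "who take any amount of study drug (PB2452 or placebo). Subjects will be analyzed as treated".

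The rule governs the main result, because SAP 9.1 states: "All efficacy analyses will primarily be based on the mITT Population". It adds: "Supportive analyses will be performed based on the ITT and Per-Protocol Population". SAP 5 defines ITT as all randomized subjects and gives no arm rule for it. SAP 7.1 says that for randomized subjects "subject disposition will be presented by randomized treatment group and total", which concerns disposition, not efficacy.

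Protocol 9.5 commits the sponsor as follows: "Any change in the plan described in this protocol will be highlighted in the SAP". The SAP has no section on changes from the protocol and no sentence that mentions this one. SAP 2 cites a protocol dated 12 August 2019. The protocol available is Version 2, dated 28 May 2021.

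The SAP also gives two mITT definitions. SAP 4.4 limits the set to randomized subjects "who take any amount of study drug and have at least one measurable post dose PRU value" and refers to Section 5 for detail, but Section 5 has no PRU condition.

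**The concern.** Counting subjects by the infusion they received gives up the protection of randomization wherever that differs from the assignment. The as-treated groups then depend partly on how dosing errors arose. If the drug works, moving a wrongly dosed subject to the arm received gives a larger difference on average, so the SAP's rule is the more favourable one to the sponsor.

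The protocol's choice looks deliberate. It applies an as-treated rule to the Safety, Per Protocol and PK sets and reserves the as-randomized rule for mITT. The SAP applies as treated to all four. Its mITT then has practically the same members and the same arm rule as its Safety Population, so the label no longer marks a randomized comparison.

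The triggering error is foreseeable. Site pharmacy staff prepare each dose (Protocol 7.2.3), and dosing errors are a listed deviation (Protocol 11.2.3). If one occurs, the two documents place that subject in different arms of the primary analysis, and nothing says which document governs.

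**Working it through.** **1. The rules side by side**

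| Set | Protocol 9.2.2 | SAP 5 |
|---|---|---|
| mITT (primary efficacy) | as randomized | as treated |
| Safety | as treated | as treated |
| Per Protocol | as treated, drawn from Safety | as treated, drawn from mITT |
| PK | as treated | as treated |
| ITT | not defined | all randomized, no arm rule |

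The arm rule for mITT and the parent set for Per Protocol differ, and SAP sections 1 to 14 flag neither.

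**2. The plan's own power.** Inputs from SAP 4.2: 150 and 50 subjects, difference 15, SD 20, two-sided 0.05, two-sample t-test.

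- SE = 20 × √(1/150 + 1/50) = 3.27
- 15 / 3.27 = 4.59
- Power from the noncentral t with 198 df = 99.5% (99.6% by the normal approximation)

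The stated figure of more than 99% reproduces.

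**3. Effect of wrong-arm infusions.** The documents give no error rate, so the counts here are assumptions. Let k be the placebo-randomized subjects given PB2452 and m the PB2452-randomized subjects given placebo. The effect is taken to follow the drug received, and the errors to be unrelated to prognosis. The difference is placebo minus PB2452.

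- As-randomized difference = 15 × (1 − k/50 − m/150)
- Each k error costs 15/50 = 0.3 points; each m error costs 15/150 = 0.1 points
- Variance in an arm with mis-dosed fraction f = 400 + 225 × f × (1 − f)
- Expected as-treated difference = 15.0 throughout

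Example, one error each way: 15 × (1 − 0.0200 − 0.0067) = 14.6. The variances are 401.5 (PB2452 arm) and 404.4 (placebo arm), so SE = √(401.5/150 + 404.4/50) = 3.28 and power is 99.3%.

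| k, m | As-randomized difference | As-randomized power |
|---|---|---|
| 0, 0 | 15.0 | 99.5% |
| 1, 0 | 14.7 | 99.4% |
| 0, 1 | 14.9 | 99.5% |
| 1, 1 | 14.6 | 99.3% |
| 3, 3 | 13.8 | 98.6% |
| 5, 5 | 13.0 | 97.3% |

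**4. Direction.** This was simulated under the same assumptions, with 20,000 trials per case. With a true 15-point effect, the as-treated difference is the larger one in about 70% of trials at (1, 1) and about 82% at (3, 3). With no effect, it favours the drug in about 50%, and both rules reject in about 5%. The as-treated rule therefore does not inflate type I error when errors are unrelated to prognosis. If they are related to prognosis, that assurance is lost; the documents give nothing from which to size this.

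**5. The post-dose PRU condition.** SAP 6.3 states: "For subjects with missing data on efficacy endpoints, no imputation will be used". A subject with no post-dose PRU value drops out of the primary t-test under either mITT definition, so the condition does not change that test. It can change the reported mITT N, the Per Protocol set drawn from mITT, and possibly the PRI endpoints.

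**The case against.** The strongest reply is that the practical effect is close to nil. Study drug is one infusion course started on Day 1, assigned through a central system, given under observation and recorded. With one error each way, the two rules reach a different significance decision in only about 0.4% of simulated trials. This stands, and it limits the argument to principle and pre-specification. It does not settle which document governs if an error occurs.

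Second, the 2019 protocol cited by the SAP may itself have said as treated. The SAP would then be out of date, not silent about a change its authors made. That cannot be checked. It would explain the mismatch with the current protocol without removing it.

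Third, the supportive ITT analysis offers a safeguard. The ITT row lacks the as-treated sentence that the other treated sets carry, and SAP 7.1 equates ITT with randomized subjects, so the natural reading is as randomized. Undosed subjects would normally contribute no post-dose PRU, so that analysis should nearly match an as-randomized mITT result. This is a fair reading, but the arm rule is inferred and the analysis is supportive only.

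Fourth, the documents already differ on the primary test: Protocol 9.3.1 uses an exact Wilcoxon test with a Hodges-Lehmann estimate, and SAP 9.1 uses a t-test with a mean difference. That is true, but it is a separate mismatch and does not excuse this one.

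**Conclusion.** The concern holds. SAP 5 replaces the as-randomized rule for the primary efficacy population with an as-treated rule, contradicts the current protocol, and does not highlight the change. It must be corrected before unblinding.

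The numerical effect is zero if nobody receives the wrong arm's infusion. With one to five errors each way, the as-randomized difference is 14.6 to 13.0 points against 15.0 as treated. These figures assume the planned effect and SD, an effect that follows the drug received, errors unrelated to prognosis, and error counts that the documents do not supply. The conclusion that the rules conflict needs none of these assumptions. The PRU condition, the Per Protocol parent set and the cited protocol version are minor consistency points.

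**What to change.** In SAP 5, state that mITT and ITT are analysed by randomized treatment, matching Protocol 9.2.2. Keep as treated for the Safety, PK and Per Protocol sets. If an as-treated efficacy result is wanted, list it as a sensitivity analysis.

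In the same revision:

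- use one mITT definition, randomized and dosed, in SAP 4.4 and SAP 5
- settle whether Per Protocol is drawn from Safety or mITT
- update the protocol version cited in SAP 2

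The cost is a few sentences before database lock. If wrong-arm dosing has occurred, the estimate may be slightly less favourable. With one error each way, as-randomized power is about 0.2 percentage points below the error-free figure (99.5% − 99.3%).

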6.1.6 End of Study

All subjects will return to the clinic at Day 35 ± 3 to complete the end of study (EOS) visit. The following procedures and assessments will be performed:

- Serum pregnancy test
- Physical examination, full, including height and weight
- Vital signs measured (SBP, DBP, RR, temperature and HR)
- 12-lead ECG
- Clinical laboratory tests including hematology, chemistry, coagulation, and urinalysis
- Blood sampling for PK: plasma PB2452, ticagrelor, and TAM PK
- Platelet biomarker sample collection (3.2% Na Citrate plasma tube)

Note: a single Qiagen PAXgene DNA tube per subject may be collected at any convenient sampling timepoint throughout the study

- Serum immunogenicity
- AEs/SAEs collected
- Concomitant medication(s)

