6.1.7 Long-term Extension

There is no long-term extension. The trial concludes at the EOS (Day 35 ± 3) visit.

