6.2 Discontinuation or Withdrawal

6.2.1 Individual Subjects

6.2.1.1 Treatment Discontinuation

A subject may withdraw consent and discontinue from the study at any time, for any reason, without prejudice to further treatment. Subject participation in the study may be stopped at any time at the discretion of the Investigator or at the request of the Sponsor, or if the study is terminated.

The Investigator may withdraw a subject from the study if the subject:

- Is non-compliant with the protocol
- Experiences a serious adverse event (SAE) or intolerable adverse event (AE) that, in the Investigator's opinion, requires withdrawal from the study
- Has laboratory safety assessments that reveal CS hematological or biochemical changes from baseline values
- During the course of the study and through the end of study develops symptoms or conditions listed in the exclusion criteria
- Requires a medication prohibited by the protocol
- Requests an early discontinuation for any reason

If a subject experiences a SAE or an intolerable adverse event (AE) that requires discontinuation in the opinion of the Investigator or as reported by the subject, then the Investigator may confer with the Sponsor regarding disposition of the subject. If a subject is discontinued from treatment because of an AE, the event will be followed until it is resolved or until the AE is stable in the opinion of the Investigator.

When a subject withdraws or is withdrawn from the study, the reason(s) for withdrawal will be recorded by the Investigator on the relevant page of the electronic case report form (eCRF). Whenever possible, any subject who withdraws from the study if willing, should continue to be followed according to the protocol. For example, if termination occurs earlier than planned (i.e., after a subject has received all or partial study drug infusion) all efforts should be made to ensure the remaining protocol visits are completed. If a subject refuses to return for the Follow-up visits, the Day 35 ± 3 visit procedures should be completed to the extent possible, and the site should try contacting the subject at least 3 times by letter, certified letter, phone call, email or other reasonable methods. All attempts to contact subjects and the final status of subjects who fail to complete final assessments will be documented in the source documents.

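### The per-protocol set requires study completion, naturally read as Day 35±3, so it excludes subjects with complete 4-hour and 48-hour efficacy data because of later events

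*SAP*

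**What the plan says.** Both documents make completion a condition of PP membership. Protocol 9.2.2 reads: "The Per Protocol (PP) population includes subjects in the safety population who do not have major protocol deviations and who complete the study". SAP section 5 uses the same condition, "who do not have major protocol deviations and who complete the study", but starts from mITT instead of the safety population.

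Neither document says what completion means for PP. The visit plan points to Day 35±3. SAP 4.5 lists "a Day 7 Follow-up visit, and a final Follow-up visit", the latter at Day 35. Protocol 6.1.6 states "All subjects will return to the clinic at Day" 35±3, and Protocol 6.1.7 adds "The trial concludes at the EOS" visit.

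The primary endpoint is the minimum percent inhibition of PRU "within 4 hours (inclusive) after the initiation of study drug" (SAP 9.1). In the schedules of events (Protocol 1.1 and Appendix 3; SAP Table 1), PRU/VASP sampling ends at 48 hours. Day 7 and Day 35 have no PRU/VASP sample.

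PP is a sensitivity analysis in Protocol 9.2.2. SAP 9.1 makes it supportive, alongside ITT, with mITT as the primary set.

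**The concern.** A per-protocol analysis should show whether the result survives removal of subjects whose conduct could have distorted the endpoint. Attendance after 48 hours cannot distort a PRU or PRI value that has already been taken. The completion condition nevertheless excludes a subject with a full set of PRU/PRI samples who leaves between 48 hours and Day 35. Nothing in either document exempts such a subject.

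Some reasons for leaving could be related to treatment. Protocol 6.2.1.1 allows withdrawal of a subject who "Experiences a serious adverse event (SAE) or intolerable adverse event (AE) that, in the Investigator's opinion, requires withdrawal from the study", and the same list includes laboratory changes, need for a prohibited medication and the subject's own request. PP membership then depends on events after randomisation and after the outcome. If PP and mITT disagreed, a reader could not tell whether endpoint-relevant deviations or follow-up attendance was the cause.

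**Working it through.** **Timing.**

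| Item | Time from start of study drug | Source |
|---|---|---|
| Primary endpoint closes | 4 hours | SAP 9.1 |
| Last PRU/VASP sample | 48 hours | Schedules of events, PD sampling footnote |
| End-of-study visit | Day 35±3 | Protocol 6.1.6, 6.1.7; SAP 4.5 |

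The PP condition runs about a month beyond the last efficacy sample.

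**The plan's own figure.** SAP 4.2 gives 150 and 50 subjects, a difference of 15 points, SD 20, two-sided alpha 0.05, and power above 99%. The standard error is 20 × √(1/150 + 1/50) = 3.27, so the noncentrality is 15/3.27 = 4.59. Power is 99.58% by the normal approximation and 99.55% by the noncentral t. The stated figure reproduces.

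**Precision under assumed non-completion.** The documents give no dropout rate, so a range is shown. The half-width of the 95% interval is t(0.975, n1+n2−2) × 20 × √(1/n1 + 1/n2).

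| Assumed non-completion | PB2452 / placebo in PP | Subjects dropped | CI half-width (points) | PP power |
|---|---|---|---|---|
| 0% | 150 / 50 | 0 | 6.44 | 99.5% |
| 5% | 142 / 48 | 10 | 6.59 | 99.4% |
| 10% | 135 / 45 | 20 | 6.79 | 99.1% |
| 20% | 120 / 40 | 40 | 7.21 | 98.3% |
| 30% | 105 / 35 | 60 | 7.72 | 96.8% |

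Before rounding to whole subjects, the interval widens by 1/√0.95 = 1.026 at 5% and 1/√0.90 = 1.054 at 10%, that is, by about 3% and 5%. Power stays near 97% even at 30%, so lost power is not the issue.

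**Selection.** Suppose a share d of one arm is excluded and their mean differs by g points from those retained. The full-arm mean is then (1−d)m + d(m+g) = m + dg, where m is the retained mean, so the PP mean differs from it by d × g. With d = 10% and g = 10 the shift is 1 point; with d = 20% and g = 20 it is 4 points, against a planned difference of 15. Both d and g are assumptions. The treatment contrast moves only to the extent that the product differs between arms, and not at all if leaving is unrelated to the 0-4 h response.

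**The case against.** The strongest reply is that nothing of consequence is lost. PP is secondary, requiring completion is a familiar convention, and deviations are assessed before unmasking. Protocol 6.2.1.1 asks that subjects who stop early still be followed where willing, so stopping the infusion is not the same as leaving the study. Subjects stay on site through Day 3 and may stay longer. These points keep the matter minor. They do not give the condition any purpose for endpoints measured by 48 hours.

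Four stronger readings might be inferred and should not be:

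- **That primary data are discarded.** They are not. A subject who leaves on Day 10 remains in mITT, and the SAP's supportive ITT analysis has no completion condition.
- **That missing Day 7 alone removes a subject.** The text does not say so. A subject who misses Day 7 but attends Day 35±3 would ordinarily count as a completer.
- **That loss will be unequal between arms.** This is possible but not shown. Protocol 2.1.4 reports Phase 1 adverse events in 17 of 48 on PB2452 (35%) and 2 of 16 on placebo (12%), but none led to discontinuation of trial drug.
- **That the two parent sets give materially different PP sets.** The safety population is everyone dosed; mITT, as defined in SAP section 5, is everyone randomised and dosed. Unless someone is dosed without randomisation, these are the same people.

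It is also fair to object that one 4-hour PP rule would be wrong. PP serves efficacy variables generally, and the duration endpoints are not limited to 4 hours. That stands, and the fix allows for it.

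**Conclusion.** The point holds as a minor one. The completion condition excludes subjects with complete efficacy data from PP because of events that follow the outcome, which weakens the only sensitivity set that the protocol names. It does not threaten the primary result.

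The size depends on assumptions, because no dropout rate is given. At 5 to 10% non-completion, 10 to 20 subjects leave PP and its interval widens by about 3 to 5%. Any shift in an arm's mean is d × g, for example 1 point for 10% excluded and a 10-point gap.

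The Day 35±3 reading is inferred from the visit schedule. Protocol 6.3 lets the trial-level end of study include longer follow-up of adverse events, which adds to the ambiguity and is a further reason not to leave completion undefined.

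**What to change.** Make three wording changes in SAP section 5 and Protocol 9.2.2:

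1. Delete the requirement to complete the study.
2. Draw PP from mITT in both documents.
3. Define PP by endpoint window. A subject qualifies with an evaluable pre-ticagrelor baseline, PRU/PRI data in the window, and no major deviation (including a dosing error) affecting PRU/PRI up to the end of the window. The window is 4 hours for the primary and other 0-4 h endpoints, and 48 hours for the duration endpoints.

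The cost is document wording and two PP flags in the analysis dataset. No added subjects, visits or samples are needed. The change should be made before database lock and unblinding, so that membership is settled without knowledge of treatment.
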